6.6.4 Serum assays

ImmunoCAP (Thermo Fisher Scientific, UK) and specific ELISAs will be used to identify Timothy grass pollen specific IgE, IgG₁, IgG₄, IgA₁ and IgA₂ in serum samples. ImmunoCAP ± ISAC microarray (Thermo Fisher Scientific) will be used to assess molecular sensitisation profiles. Additionally, serum will be assessed for its ability to inhibit both IgE-mediated facilitated allergen binding (FAB) to B-cells²¹ and allergen-induced basophil histamine release.

6.6.5 Serum Archive

Serum will be aliquoted and banked from study participants who provide informed consent for storage of their samples for a minimum of ten years for future studies as novel serum-based assays of immune tolerance become available.

6.6.6 Nasal fluid

Nasal fluid will be assayed for inflammatory mediators and local antibodies.

Measured analyses will include some/all of the following:

- The mast cell degranulation marker tryptase will be measured by ImmunoCAP.
- IFN- γ , IL-4, IL-5, IL-6, IL-9, IL-10, IL-12p70, IL-13, IL-17A, IL-23, IL-25, IL-27, IL-33, MDC, eotaxin, TARC, RANTES, CXCL-8 (IL-8) will be measured by MILLIPLEX MAP Human Cytokine/Chemokine assay (Merck Millipore, UK).
- TSLP will be measured by MILLIPLEX assay.
- Specific IgE, sIgG₁, sIgG₄, sIgA₁, sIgA₂ and their molecular binding profile to timothy grass pollen will be assessed by ImmunoCAP and/or ISAC (Thermo Fisher Scientific/Phadia, Sweden).
- Inhibitory activity for Fc ϵ R1 - dependent basophil activation will be assessed by measuring expression of surface CD63, CD203c, and intracellular Diamine Oxidase (DAO) by flow cytometry.

- Additional mediator/antibody/cytokine assays deemed relevant and of scientific interest that become apparent during/after the course of the study may be performed on the collected samples.

6.6.7 Blood samples

Samples will be taken at the time points indicated previously. We plan to perform the following analysis:

- In collaboration with [name] and [name] (ALK-Abello, Denmark): investigation of changes in B cell repertoire and receptor editing following AIT by advanced gene sequencing techniques.
- With [name] (King's College, London): high-throughput sequencing of B cell variable regions, grass pollen-specific antibody cloning and protein binding by Surface Plasmon Resonance.
- *Ex vivo* allergen induced basophil activation and histamine release by flow cytometry (BD Biosciences).
- T-cell assays will be performed as described above (section 6.6.3). Additionally, 48 hour CpG/LPS-stimulated CD4⁺ cell IL-10 and IL-35 release and ICOS-Ligand expression will be assessed.
- A time course analysis of all FoxP3⁺ T regs, IL-10⁺, IL-35⁺ and TGF- β ⁺ T regs by flow cytometry.
- Cytokine gene methylation assay will be performed on freshly isolated T cells. Genomic (g) DNA will be isolated from T cells.
- Investigation of the time course of the effect of grass pollen-AIT on putative innate lymphoid cells by 8-colour flow cytometry – lineage negative, CRTH2⁺ CD127⁺CD25⁺ST2⁺IL-13⁺CD25R⁺ CD161⁺cells.

- Fresh blood will be used for whole blood flow cytometry using monoclonal antibodies to identify activated basophils and dendritic cells (see below).

Antibody	Identified cell subset

Panel 1 CD1c- APC-Cy7 CD11c -V450 CD123- PerCP-Cy5.5 CD303- FITC CD80-PE-Cy7 CD86-APC HLA-DR -V500 OX40L-PE
 
Panel 2 CD1c-APC-Cy7 CD11c-V450 CD123-PerCP-Cy5.5 CD303-FITC TSLP-R-APC FcεRI-PE-Cy7 ICOS-L-PE
	Plasmacytoid dendritic cells and activation markers
CD3-PE-Cy7 CD294(CRTH2)-PE CD203c-PercP-Cy5.5 CD303-APC CD107a-Pacific Blue CD63-FITC	Basophils plus activation and degranulation markers

- Whole blood flow cytometry using monoclonal antibodies will be used for phenotypic regulatory T, B and dendritic cells (see below).

Antibody		Identified cell subset
CD45RO CD3 CD4 CD8 CCR7 CRTH2	GATA-3 T-bet IL-12Rb2 IFN- γ R CD1c CD11c	Th1/Th2 cells
CD45RO CD3 CD4 CD69	CRTH2 CCR7 CD40L GATA-3	Activated Th2 cells
CD4 CD25 CD45RO CD127 CD8 CD39 IL-35 IL-10 TGF- β IFN-g	Foxp3 CD39 Helios pSTAT-5	Regulatory T cells (panel 1)
CD62L LAG-3 CD279 (PD1) GARP Galectin-1 IL-12p35 EBI-3	CTLA-4 IL-10 TGF- β IFN- γ CD161 SAT1B LARP	Additional regulatory T cell markers

CD4 CXCR5 PD1 Bcl6 Blimp IL-21		T follicular helper cells
CD19 CD5 CD25 CD38	CD279 IL-10 TGF- β	B regulatory cell
CD123 CD303 CD80 CD86 HLA-DR	DC-SIGN OX40L ICOS-L PD1-L IL-27	Activated dendritic cells

- FluoroSpot assays will be used to determine proportions of IL-10+CD19+CD5+ B cells.
- Phenotypic characterisation of regulatory B cells will be performed on whole blood and PBMCs. IL-10-producing B cell subsets will be assessed in the two groups. Stimulated B cells will be surface and intracellular stained with anti-human CD5, CD24, CD38, PD1, CD27 and IL-10 (BD bioscience, USA) and analysed by flow cytometry. Further characterisation will as well take place by flow cytometry and will be confirmed by RT-PCR. Enumeration of Bregs and frequency of allergen-specific B cells will be performed.
- We will perform deep sequencing of the TCR β repertoire using a previously validated Repertoire Sequencing (REP-SEQ) assay^{26, 27, 28} in PBMCs samples. Briefly, multiplex PCR is performed on genomic DNA with primers targeting all V β and J β genes. High-throughput measurement of clonotype, function, and abundance of single T cells called TELS (TCR β -effector linkage sequencing), which combines microfluidics and next-generation sequencing to encapsulate and genetically analyse hundreds of thousands of single cells per hour. After bioinformatics analysis, TELS data provides a simultaneous measure of TCR β CDR3 sequence, effector gene activity, and abundance of T cell subpopulations from mixed cell samples with high sensitivity and high throughput.

6.6.8 Nasal brushings

Nasal brushings will be performed according to the timelines mentioned above and used for the different analyses described below.

- RNA will be extracted from cells obtained by nasal brushings (RNeasy, Qiagen), followed by creation of cDNA and real-time PCR to quantify gene expression by automated analysis. Levels of expression of a range of allergic/inflammatory genes, regulatory genes and structural genes will be used to verify patterns of cytokine recovery from within nasal fluid. Patterns of gene expression can be used to identify the presence of different cell types within the superficial nasal mucosa. Genes of interest will include those for epithelial-cell derived chemokines: MDC, TARC, eotaxin, RANTES; adhesion molecules including ICAM-1; cytokines including IL-8 and GM-CSF. Genes of interest from migratory effector cells will include IL-4, IL-5, IL-9, IL-13, IFN- γ , IL-10, TGF- β , IL-25, IL-22, IL-33, IL-35, IL-27, GATA-3, STAT-6, STAT-5, T-bet, and FOXP3.
- Genomic DNA will be isolated from cells using an appropriate isolation kit (QIAamp DNA Mini Kit, Qiagen). Global DNA methylation will be recorded (Methylamp Global DNA methylation Quantification Kit, Epigentek Group, Farmingdale, NY, USA). Individual candidate gene methylation status will be measured using methylation specific PCR.
- Cells collected from nasal brushings will be immunostained with anti-human CD3, CD303, CD294 (CRTh2), DAO, CD203c, CD63 (BD Biosciences, San Jose, CA). Non-activated and activated basophils will be identified as CD203c^{dim} CRTh2⁺ and CD203c^{bright} CRTh2⁺ cells, respectively. Additionally, activated cells will also be identified as CD63⁺ and CD107a⁺ CRTh2⁺ basophils. DAO⁺ CRTH2⁺ basophil will also be identified. Analyses will be performed using BD FACSDiva V6.1.1 software (BD Biosciences).

- Putative innate lymphoid cells, ILCs, will be Nuocytes will be assessed by 8-colour flow cytometry – lineage negative, CRTH2+ CD127+CD25+ST2+IL-13+CD25R+ cells.

6.6.9 Nasal biopsy

Nasal biopsies will be taken at the time points described. Biopsy specimens will be processed as follows:

- In collaboration with [name], we will investigate changes in B cell repertoire and receptor editing following AIT.
- [name] will carry out high-throughput sequencing of B cell variable regions and extract and isolate individual B cells for determining binding affinities of peripheral and nasal grass-pollen specific antibodies.
- For immunohistochemistry, one biopsy will be snap-frozen in liquid nitrogen and stored at -80°C. 6µm cryostat sections will be cut and stained, and examined by immunofluorescence for the following markers: Phl p5, IgA2, CD138 and CD20 to detect grass-pollen specific IgA-expressing plasma and memory B cells; TGF-β1, IL-10, IL-21, IL-35, IL-27, FoxP3, CD3 to detect phenotypic T regulatory cells; IL-10, CD19, CD5, ICOS-Ligand as markers of phenotypic B regulatory cells.
- For PCR analysis, total mRNA will be extracted from biopsy tissues using a suitable tissue mRNA isolation kit (Qiagen tissue mRNA isolation kit, Qiagen). Amplified cDNA will be produced from isolated mRNA by RT-PCR. Specific DNA primers will be used to assess the expression of the I exon germline gene of the IgA2 gene locus (Iα2) and the C region gene for IgA2 (Cα2) in the form of germline transcripts (GLTs) and switch circle transcripts (SCTs). The origin of these transcripts - generated by class switch from IgM, IgG, IgA1 or IgE - will also be ascertained according to methods previously described¹¹. Identified transcripts will undergo nucleotide sequencing and Southern blot analysis.

Activation-induced cytidine deaminase (AID), RAG1 and RAG2 expression will also be assessed by PCR as markers of antibody gene class switch recombination.

- One biopsy piece will be placed in appropriate medium before undergoing cell separation from solid tissue matrix, followed by magnetic bead enrichment and single cell FACS sorting to identify grass-pollen specific IgA expressing B cells. Cloning of allergen specific IgA, followed by affinity measurement and evaluation in functional assays will be carried out as above.
- For High-Throughput sequencing of local and peripheral B cell repertoires RNA will be isolated from nasal biopsies and peripheral blood mononuclear cells and converted to cDNA. Heavy (IgA, IgG, IgM and IgE) and Light (Ig κ and Ig λ) chain variable region transcripts will be amplified using semi-nested, isotype-specific PCR. Sample-specific multiplex identifier (MID) adaptor sequences will be incorporated into 2nd round PCR products to allow pooling of samples. Pooled PCR products will be purified by gel electrophoresis and sequenced on the GS FLX+ system.
- For Isolation of nasal B cells and antibody cloning, single cell suspensions of nasal biopsy tissue will be obtained by mechanical dissection and enzymatic digestion. Cells will be stained with antibodies against B cell surface markers and single B cells will be individually sorted for single-cell RT-PCR. Matched heavy and light chain transcripts will be amplified by nested, isotype-specific PCR. PCR products will be purified and sequenced by capillary sequencing. Selected sequences will be re-amplified by PCR and cloned into a human expression vector containing the corresponding heavy and light chain constant region genes. Recombinant antibodies will be stably expressed in mammalian cells and purified from cell culture supernatant.
- The affinities of recombinant nasal and purified, polyclonal plasma antibodies for individual grass pollen allergens will be measured using Surface Plasmon Resonance (SPR). Purified antibodies will be captured and immobilised using anti-isotype antibodies bound to a SPR sensor chip. Initial experiments will

determine their specificity for individual grass pollen allergens at a single concentration. Detailed kinetic analysis using a concentration series of the relevant individual allergens will then be used to derive association (k_{on}) and dissociation (k_{off}) rates. These will be used to calculate antibody binding/affinity constants.

6.7 Recording, Managing and Reporting Adverse Events

The PI is responsible for the detection and documentation of events meeting the criteria and definition of an adverse event (AE) or adverse reaction (AR) as described under sections 6.7.1.1 – 6.7.1.7 in this protocol. All AEs, ARs and severe adverse events (SAEs) will be recorded on the appropriate case report forms (CRFs) and the specific serious adverse events (SAE) will be reported as soon as possible and within 24 hours. Data will be entered into MHRA approved Clinical Trial database 'InForm'. This section defines the types of AEs and ARs and outlines the procedures for appropriately collecting, grading, recording, and reporting them. Information in this section complies with JRCO/SOP/001 SOP concerning Recording, Managing and Reporting Adverse Events in the UK³¹. A 24 hour contact phone number will be given to all participants. Day to day management of the study will be coordinated by [name].

6.7.1 Definitions

6.7.1.1. Adverse Event

An AE is any occurrence or worsening of an undesirable or unintended sign, symptom, laboratory finding, or disease that occurs during participation in the trial and which does not necessarily have a causal relationship with the treatment administered. An AE will be followed until it resolves or until 30 days after a participant terminates from the study, whichever comes first. All AEs will be reported as specified in section 6.7.6.4. During the study it is anticipated that all participants will experience seasonal symptoms of itching sneezing, watery discharge, nasal congestion, and eye symptoms, with or without wheezing from mid-May through mid-July. These are usual symptoms of SAR which represent their entry criteria for the study. In addition, participants will have free access to anti-allergic drugs that include antihistamines, intranasal corticoid

steroids, and eye-drops for relief of their symptoms. This data will be captured in the Questionnaires throughout the pollen season (i.e. Visual Analogue Scale, and Rescue Medication Score). These symptoms and requirements for rescue medications will not be reported as AEs.

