6.4.4 Special Warnings and Precautions for Use

In case of oral surgery, including dental extraction, treatment with Grazax® should be stopped for 7 days to allow healing of the oral cavity. Mild to moderate local allergic reactions such as itching or swelling of the mouth may occur during treatment. If significant local adverse reactions occur treatment with antihistamines should be considered. Rare cases of severe systemic allergic reactions have been reported with Grazax® use. Therefore medical supervision at the start of treatment is an important precaution. All participants will be provided with an emergency telephone contact number for study personnel with 24 hour availability. The onset of systemic symptoms may include flushing, itching in the extremities and other areas of the body, general discomfort and agitation. In cases of severe systemic reactions including angioedema, difficulty swallowing or breathing, throat fullness or hypotension, Grazax® should be discontinued and a physician contacted immediately. Severe systemic reactions may be treated with adrenaline. Treatment with Grazax® should remain withheld until evaluation by a study physician. If participants with concomitant asthma experience symptoms and signs indicating asthma deterioration, treatment should be discontinued and a study physician consulted immediately. Grazax® contains fish-derived gelatin. The available data have not indicated an increased risk of allergic reactions in severe

fish allergic patients. However as a precaution, patients will be asked during screening whether they are allergic to vertebrate/finned fish. If the history is positive, a skin test and/or specific IgE test to vertebrate/finned fish will be requested and if positive the subject will not be included in the study.

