6.4.8 Concomitant medication

6.4.8.1 Permitted Medications

The following rescue medications will be provided. These medications are considered standard of care and will be provided approximately 2 weeks before the start of the pollen season (May 2014) and throughout the pollen season:

- Antihistamine (e.g. desloratidine).
- Nasal corticosteroid (e.g. fluticasone propionate aqueous nasal spray).
- Ophthalmic antihistamine (e.g. olopatadine eye drops).

Use of the following rescue medications will be provided by the study only after participants are evaluated by the investigator. Evaluations may occur by phone contact or clinic visit.

- Oral corticosteroid (e.g. prednisolone).
- Short-acting beta-agonists (e.g. salbuterol).
- Inhaled corticosteroids (e.g. fluticasone).
- Combination long-acting beta-agonists or steroids (e.g. salmeterol/fluticasone).

Refer to **Appendix 7** for required medication washout periods prior to screening, nasal challenges and biopsies (V-1, V0b, V5, and V7).

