Appendix 5: Symptom and Medication Score

Please complete weekly on Wednesday during the pollen season from beginning of May until the end of July.

Symptom Score:

“How do you assess the severity of your hay fever symptoms when they were at their most severe during the last week (tick each single symptom)?”

Rhinoconjunctivitis / Hayfever Symptom		Symptoms			
		0 (None)	1 (Mild)	2 (Moderate)	3 (Severe)
Nasal Symptoms					
1	Runny nose				
2	Blocked nose				
3	Sneezing				
4	Itchy nose				
Eye Symptoms					
1	Itchy eyes				
2	Watery eyes				

Medication score:

“On how many days did you require use of rescue medications in the last week (tick each single medication)?”

Rescue medication	Number of days used			
	0 days	1-2 days	3-4 days	5 or more days
Antihistamine tablets				
Nasal spray				
Eyedrops				

Symptom and Medication Score (SMS) = (Symptom score/6 + Medication score/6)/2

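### In-season wheeze is exempt from AE reporting because the questionnaires are said to capture it, but none asks about the chest or inhalers, so non-serious asthma worsening may be missing from the AE tables

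*Protocol*

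**What the plan says.** Protocol 6.7.1.1 first defines an AE broadly, so that worsening of a symptom or disease counts. It then describes the expected seasonal picture: nose and eye symptoms "with or without wheezing from mid-May through mid-July". It notes free access to "anti-allergic drugs that include antihistamines, intranasal corticoid" steroids and eye-drops. The reason given for not reporting is this: "This data will be captured in the Questionnaires throughout the pollen season (i.e. Visual Analogue Scale, and Rescue Medication Score"). The paragraph ends: "These symptoms and requirements for rescue medications will not be reported as AEs".

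The exclusion then carries forward. Protocol 6.7.6 and 6.7.6.2 limit AE recording and collection to events not excluded by 6.7.1.1 and 6.7.1.2. SAP 8.1 assesses safety through reported AEs, and SAP 8.2 includes a summary category for AEs that ended study treatment.

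Three other sections bear on asthma:

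- Protocol 6.3.2 admits people with mild seasonal asthma.
- Protocol 6.4.4 says: "If participants with concomitant asthma experience symptoms and signs indicating asthma deterioration, treatment should be discontinued and a study physician consulted immediately".
- Protocol 6.4.8.1 has a second list, covering oral corticosteroids, short-acting beta-agonists, inhaled corticosteroids and combination inhalers. It introduces the list with: "Use of the following rescue medications will be provided by the study only after participants are evaluated by the investigator".

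**The concern.** The exemption is reasonable for nose and eye symptoms, because the weekly questionnaires record them. It would be unsound for any symptom that it names but that no questionnaire measures. Wheeze is named. If no instrument records it, the event is neither an AE nor a questionnaire outcome.

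The protocol itself treats asthma deterioration as a safety matter. An event that led to stopping the tablet under 6.4.4 might still be regarded as exempt under 6.7.1.1, and so be absent from the SAP 8.2 count of AEs that ended treatment. Exempt wheeze also need not reach the causality step in 6.7.3, where a link to the tablet would be judged. Documenting the presence and severity of side effects is secondary objective 3.

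**Working it through.** The plan gives no figure on this point to reproduce. The check is an item count, one score calculation and a comparison of sections.

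**1. Does any questionnaire record wheeze or an inhaler?**

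| Instrument | Content | Chest items | Inhaler rows |
|---|---|---|---|
| Appendix 5, symptoms | 4 nasal + 2 eye = 6 | 0 of 6 | – |
| Appendix 5, medication ("On how many days did you require use of rescue medications in the last week") | Antihistamine tablets, nasal spray, eyedrops = 3 | – | 0 of 3 |
| Appendix 3, miniRQLQ | 14 items on activities, practical problems, nose, eyes and general symptoms | 0 of 14 | – |
| Appendices 1, 2 and 4 | Overall hay fever only | 0 | – |
| SAP 7.3.1 medication score | Antihistamine tablets and eye drops, nasal spray, prednisone | – | 0 |

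The SAP score gives prednisone 3 points per day, but the Appendix 5 form has no row on which to enter it.

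**2. What would the seasonal score show?** Appendix 5 defines SMS = (symptom score/6 + medication score/6)/2. Take a participant whose only problem in June is wheeze treated with an inhaler. Both component scores are 0, so SMS = (0/6 + 0/6)/2 = 0, the same as for a participant with no symptoms.

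**3. How long is the window?** Taking mid-May as 15 May and mid-July as 15 July (an assumption), the window is 17 days in May + 30 in June + 15 in July = 62 days, or 62/7 = 8.9 weeks. It falls in the only pollen season of the blinded phase.

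**4. Is there a severity limit?** In 6.7.1.2, tablet, sponge and skin-test reactions are exempt only until they disturb sleep or daily activities. The seasonal exemption in 6.7.1.1 has no such limit.

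**5. Which drugs does the exemption cover?** Read alone, 6.7.1.1 names three kinds of drug, which match the three rows in Appendix 5. Section 6.4.8.1 uses the same term, rescue medications, for the asthma drugs. The text does not settle which sense applies.

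**6. Do other routes close the gap?**

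- Serious events: 6.7.6.2 collects these under a separate sentence without the exclusion. This route is intact.
- Concomitant medication: recorded on the CRF (SAP 9.1) and scheduled at the visits (SAP 10.2.1), so inhaler use should appear there. It is summarised as counts under other analyses, without grade or causality.
- Daily diary (Appendix 9): has a free-text field for other symptoms, but it sits beside questions on tablet reactions. SAP 7.3.1 analyses the diary as symptoms following the tablet.
- WAO grading (6.7.2): applies to systemic reactions to the tablet or procedures, so the wheeze must first be recognised as one.

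These routes keep traces of the event. None of them guarantees that a non-serious episode of wheeze is counted as an AE.

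**The case against.** The best defence is that the exemption covers only the usual symptoms that qualified people for the trial. Worsening of a disease remains an AE under the opening definition of 6.7.1.1, so real asthma deterioration would still be reported. A stop for asthma would also fit the reason in 6.3.7 concerning an AE that poses unacceptable risk, and would reach the SAP 8.2 table that way. Exclusion criteria remove perennial asthma on regular inhaled steroids, low FEV₁ and recent emergency asthma care. The exemption applies alike to both blinded arms and does not touch the primary endpoint. All of this is fair, and it is why the conclusion is that events may be missing, not that they will be. It does not rescue the stated rationale: wheeze is exempt by name, without a limit, on the strength of a record that does not exist.

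Several stronger readings are tempting, but the documents do not support them:

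- **Asthma treatment is exempt.** This needs 6.7.1.1 to be read through 6.4.8.1. The free-access drugs named in 6.7.1.1 exclude inhalers, so the reach is ambiguous and not established.
- **In-season asthma disappears from the safety data altogether.** Serious events and medication records remain, and there are partial routes for the rest.
- **A severe tablet reaction could escape the Grade 3 criterion in 6.3.7.** That criterion turns on the reaction itself (a fall of over 40% in PEF or FEV₁ that does not respond easily to a bronchodilator, and/or laryngeal oedema with stridor), not on an AE label. Filing such an event as ordinary hay fever is implausible.
- **The gap affects on-treatment safety of the active arm in 2016.** Its 24 months of treatment, begun in January to April 2014, end before that season.

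Other remedies exist, such as adding a wheeze item and an inhaler row, or borrowing the limit from 6.7.1.2. Questionnaire rows would record the data, but without causality or grade and outside the AE tables.

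**Conclusion.** The point holds as a reporting gap. The questionnaire rationale in 6.7.1.1 is sound for the nose and eyes and fails for wheeze and inhalers. Following the plan as written can leave non-serious wheeze or asthma worsening out of the AE tables, including the count of AEs that ended treatment, for about 62 days in the one blinded pollen season.

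The number of events at stake cannot be estimated. The documents neither state nor cap how many participants have seasonal asthma, so the number could lie anywhere from none to all of those randomised (at least 44 planned). The conclusion assumes that site staff apply the exemption literally; staff who read it narrowly would lose less. Serious events, concomitant medication records and the primary endpoint are not affected.

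**What to change.** In 6.7.1.1, limit the exemption to the nose and eye symptoms and the three rescue drug classes that Appendix 5 records. State that wheeze or asthma worsening, and any use of the 6.4.8.1 drugs that need investigator evaluation first, is recorded as an AE with grade and causality.

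Reconcile 6.4.4, 6.4.8.1, 6.7.1.1, 6.7.6.2 and Appendix 5 so that an event that leads to stopping treatment is always counted as an AE. This concerns recording only. It does not say when treatment should be stopped or which drug should be given.

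SAP 8.2 contains no seasonal exemption, so it has none to remove, and its tables will pick up the added events.

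The cost is a wording amendment, a few more AE forms and a higher reported AE count in both arms. The extra work is small, because the investigator already evaluates participants before those drugs are supplied.
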